SFD to be 3.6 and within-subject correlation (ICC) of 0.3. We calculated power for the intervention effect on SFD while justifying repeated assessments for outcomes.^{64,65} A sample size of 150 subjects per group will obtain 90% power to detect a difference of 0.8 SFD, and 80% power to detect a difference of 0.7 SFD at a two-sided 5% significance level. This difference would be clinically meaningful and consistent with prior successful interventions.^{7,66-68} We found that 194 of the children from our prior SB-TEAM study had moderate-severe persistent or difficult to control asthma at baseline, and would be eligible for TEAM-UP. In addition, in our prior office-based study we enrolled >400 children with moderate-severe asthma from the main primary care practices in urban Rochester over 4 years. Our prior studies enrolled >70% of eligible subjects. Thus, we can conservatively enroll 90 subjects/year, which is more than adequate for sample size requirements. We anticipate <15% attrition (attrition <5% in prior studies). We therefore expect complete data on at least 150 children per group.

Primary Analysis:

The primary analysis of this study aims to assess the effectiveness of the TEAM-UP intervention in reducing asthma morbidity (including symptom-free days post-intervention (follow-ups at 3 mo, 5 mo, 7 mo and 12 mo as the primary outcome) compared to an enhanced care comparison group in school age children with moderate-severe persistent asthma or uncontrolled asthma. We will use graphs and descriptive statistics to summarize the primary and secondary outcomes by intervention group at each assessment point (baseline, 3, 5, 7 and 12 mos). We will assess for differences between groups at baseline despite randomization in key characteristics (i.e.; age, race, ethnicity, insurance, caregiver education, smoke exposure.) These comparisons will enable the identification of covariates to be controlled when evaluating the treatment effect. If distributional assumptions associated with a particular statistical procedure are violated, appropriate transformations will be made or non-parametric alternatives used. In accordance with the intention-to-treat principle,⁶⁹ all randomized subjects will be analyzed within the group to which they were assigned. Minimal crossover is expected. Hypothesis-driven comparisons will be made to control the family-wise type I error rate at 0.05 (two-sided) for the primary hypothesis.

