We will consider the total cost of initiating and maintaining the program as well as the incremental cost-effectiveness ratio (ICER) of TEAM-UP versus EC. The ICER is the difference in cost between the 2 study groups relative to the difference in the number of SFDs gained between the 2 groups. The main outcome for the analysis from the societal perspective will be the ICER, defined as:

$\Delta\text{Medical} + \Delta\text{Productivity} + \$\text{Program} / \Delta\text{SFD}$, where $\Delta = (\text{TEAM-UP}) - (\text{EC})$. We will bootstrap⁷⁸ the ICER to estimate standard error and to evaluate uncertainty around the point estimate. We will compare the ICER to similar estimates from the literature.^{79,80} We will plot an acceptability curve, linking various values of SFD to the probability of TEAM-UP being cost-effective.⁸¹ The study from the Medicaid perspective will use the cost-benefit approach to economic evaluation. Benefits include the net difference in medical costs between children in TEAM-UP and EC and account for a potential reduction in unplanned visits as well as an increase in preventive visits. The cost is equivalent to the cost of the program (*Net Monetary Benefit* = $\Delta\text{Medical} - \$\text{Program}$).

Process Evaluation:

Descriptive statistics will be used for the process evaluation, looking in particular at the efficiency of the program implementation along with the responses from parents, PCPs, specialists, and school nurses and administrators about convenience, scheduling, satisfaction, and sustainability.^{82,83} We will evaluate RE-AIM (*Reach, Effectiveness, Adoption, Implementation, Maintenance*) metrics to evaluate the program. To estimate *Reach* we will determine the proportion of eligible children with moderate-severe persistent asthma who participate, and will use data from screening forms to characterize those who do and do not participate. To estimate *Effectiveness*, we will conduct intent to treat analyses of the primary outcome (SFD), absenteeism, and quality of life. We will use school data as well as surveys from PCPs,

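### The bootstrap standard error planned for the ICER does not converge; report net benefit or percentile limits from the same replicates instead

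*Combined protocol and SAP*

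**What the plan says.** The Cost Effectiveness Analysis section defines the measure as a ratio. The numerator adds the medical and productivity cost differences and the programme cost; the denominator is ΔSFD. The section gives this ratio a leading role: "The main outcome for the analysis from the societal perspective will be the ICER".

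Two treatments of uncertainty follow. The plan bootstraps "the ICER to estimate standard error and to evaluate uncertainty around the point estimate", and it adds a second display: "We will plot an acceptability curve, linking various values of SFD to the probability of TEAM-UP being cost-effective".

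The section names no percentile, Fieller or net-benefit interval for the ICER. It gives no number of replicates and no rule for replicates in which ΔSFD is near or below zero. The net monetary benefit that it does define belongs to the separate Medicaid analysis (medical cost difference less programme cost) and places no value on symptom-free days.

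**The concern.** A standard error is a useful summary only if the quantity has a finite variance for it to estimate. When the denominator of a ratio is approximately normal with positive density at zero, the ratio has no finite variance. A finite set of bootstrap replicates always returns a number, but that number reflects the handful of replicates closest to a zero denominator. Change the seed and it changes; add replicates and it tends to grow. Replicates with negative ΔSFD raise a further problem: higher cost with fewer symptom-free days gives a ratio of the same sign as lower cost with more.

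At stake is the precision quoted beside the ICER. Cost-effectiveness is one of the listed Study Objectives, and the plan compares the ICER with published estimates. A reader would take the standard error as a measure of how well the trial determined the ICER, when its size would be largely an accident of the computation.

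**Working it through.** **Inputs from the Sample Size and Power Justification.** The plan assumes a pooled SD of "SFD to be 3.6 and within-subject correlation (ICC) of 0.3", with four follow-ups (3, 5, 7 and 12 months). It states that "A sample size of 150 subjects per group will obtain 90% power to detect a difference of 0.8 SFD"; its second stated pair is 0.7 SFD with 80% power, and the test level is two-sided 5%. Total enrolment is 360, or 180 per arm.

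**Assumptions not in the documents.** ΔSFD is the time-averaged contrast, observed at 0.8. The cost-difference coefficient of variation (CV, its standard error divided by its value) is 20-50%. Cost and SFD are independent. Results are multiples of the point ICER, so multiplying SFD or cost by a constant does not alter them.

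**The plan's own figure.** Effective SD = 3.6 × √((1 + 3 × 0.3)/4) = 3.6 × √0.475 = 2.481. SE(ΔSFD) = 2.481 × √(2/150) = 0.2865. At 0.8, z = 0.8/0.2865 = 2.79, which gives power of 79.7% against the stated 90%; at 0.7 it gives 68.6% against the stated 80%. The stated power is thus not recovered by this direct route. Because that could make the denominator look too weak, four versions of it are carried forward:

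- Unadjusted, 150 per arm: SE 0.2865, z = 2.79.
- Baseline-adjusted, 150 per arm (baseline correlation assumed 0.3): 3.6 × √(0.475 − 0.09) × √(2/150) = 0.258, z = 3.10.
- SE implied by the stated 90% power: 0.8/(1.960 + 1.282) = 0.247, z = 3.24.
- Baseline-adjusted, 180 per arm, no attrition: 3.6 × √0.385 × √(2/180) = 0.235, z = 3.40.

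At z = 2.79, 0.26% of replicates have ΔSFD at or below zero; at z = 3.24, 0.06%.

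**Repeating the bootstrap.** For each version the bootstrap was repeated over 400 seeds, drawing ΔSFD and ΔCost from normal distributions and recording the SD of the ratio. With 1,000 replicates, SE as a multiple of the ICER:

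| Denominator | 5th percentile | Median | 95th percentile |
|---|---|---|---|
| Unadjusted, 150 per arm | about 1.1 | about 2.8 | 20-40 |
| Baseline-adjusted, 150 per arm | 0.7-0.9 | 1.3-1.5 | 13-17 |
| Implied by stated 90% power | 0.6-0.8 | about 1 | 5-9 |
| Baseline-adjusted, 180 per arm | 0.5-0.7 | 0.7-0.9 | 5-6 |

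Ranges within a cell cover the assumed cost CVs. The upper ends are rough: for the stated-power row, separate sets of 400 seeds gave values from 5 to 12.

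**More replicates do not help.** With 5,000 replicates the median rises to 5.5-6 in the first row and 1.9-2.0 in the third, and it rises in the other two rows as well. At z = 2.79 and an intermediate cost CV of 25%, the median goes from 2.6 to 8.1 to 34 as replicates go from 1,000 to 10,000 to 100,000. The delta-method value for that setting is √(0.25² + (1/2.79)²) = 0.44. A cost-SFD correlation of ±0.5 changes the sizes but not the pattern.

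**Resampling children.** A nonparametric bootstrap of 150 per arm with skewed costs (observed ΔSFD 0.8, SE 0.2865, 1,000 replicates, 60 seeds) gave an SE from 0.88 to 21.6 times the ICER at cost CV 25%, and from 1.0 to 679 times at 50%.

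**The alternatives from comparable replicates.** Value an SFD at twice the ICER. In units of the cost difference, the SE of incremental net benefit at z = 2.79 and cost CV 20% is √((2/2.79)² + 0.2²) = 0.74. This is finite, and across seeds it varied only from 0.72 to 0.77 with 1,000 replicates. The 97.5th percentile of the ratio ranged from 3.1 to 3.5 times the ICER with 5,000 replicates. In the nonparametric run at cost CV 25% with 10,000 replicates (15 seeds), the probability of being cost-effective ranged from 0.904 to 0.912, while the SE of the ratio ranged from 2.8 to 246 times the ICER.

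**The case against.** The strongest reply is that the section already contains what is needed. The acceptability curve is the display most relevant to a decision, and it is well behaved. The bootstrap's second stated purpose, evaluating uncertainty, is broad enough to include percentile limits. What is left is one phrase in a secondary economic analysis. This stands as a limit on scope: neither the bootstrap nor the curve is at fault. It does not remove the defect, because the plan still commits to a standard error and specifies no percentile limits.

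A second reply is that the unadjusted denominator is unfavourable, since the Primary Analysis adjusts for baseline SFD and includes all randomised children. That also stands, and it is why four denominators are shown. The more favourable ones reduce the median to roughly a third to a half of the unadjusted value, but the instability persists in every row.

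A third reply is that the documents do not say how SFDs are accumulated for the ICER, and give no cost variance or cost-SFD correlation. This is fair. The exact multiples are therefore illustrative; the failure to converge comes from the denominator and does not depend on them.

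A reader might also infer that the plan will set a mean ± SE interval against published ICERs. It does not say so: it plans to compare the ICER itself with the literature and describes no interval or test built on the standard error.

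**Conclusion.** The concern holds, confined to the standard error reported for the ICER. That standard error would depend on the seed and on an unstated number of replicates. With 1,000 replicates, the 95th percentile across seeds is several times to more than ten times the 5th under all four denominators, and more replicates raise the median. This rests on an observed ΔSFD of 0.8 and the assumed cost CV and independence. A smaller observed effect makes it worse: at 0.6 with the unadjusted SE, the median is 12-13 times the ICER.

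Two stronger readings are tempting and unsupported. One is that the whole uncertainty analysis for cost-effectiveness is arbitrary; the acceptability curve from the same replicates is stable, and so are percentile limits by comparison. The other is that the effectiveness result is compromised; the primary SFD analysis does not use the ICER. The mismatch between the stated and recomputed power is a separate matter, and this point does not depend on it.

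**What to change.** In the Cost Effectiveness Analysis section, delete the standard error of the ICER. Resample children within arm, keeping each child's cost and SFD together, and state the number of replicates. From those replicates report incremental net benefit (value per SFD × ΔSFD − ΔCost) with a percentile 95% interval over a stated range of values per SFD, beside the acceptability curve already planned. Give it a name distinct from the Medicaid net monetary benefit, which does not value SFDs.

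If an interval for the ICER itself is wanted, use percentile or Fieller limits and state the share of replicates with ΔSFD at or below zero, where the ratio cannot be read.

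The cost is a few sentences of SAP wording, with no new data and no additional resampling. The downside is that there will be no single standard error to quote beside the ICER.

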
Our existing community-wide telemedicine program receives referrals for visits from parents or providers. A Clinical Telehealth Assistant (CTA) collects medical data and images from the child at their school, daycare, or home using mobile units, and stores the data for the provider in a secure internet system. The stored data enable clinicians to provide assessments based on a full complement of clinically-important information. Equally important, providers can engage parents in counseling through remote audiovisual technology. The provider can complete visits from their office at their convenience, and communicate with the caregiver by telephone to collect additional information and discuss the treatment plan. Visits can also be done in 'real-time'; connecting parties via videoconference. The system enables children to be seen by a provider without making a trip to the office, thus eliminating a significant barrier to care.^{51,52} Telemedicine visits are reimbursed by local payers, including Medicaid Managed Care (which covers 75% of Rochester's children), making it sustainable. Telemedicine is efficient, cost-effective, and safe, and is now used in urban and rural areas worldwide.⁵³⁻⁵⁵ Telemedicine is also integrated into many school districts, and a systematic review endorsed its use to meet the healthcare needs of underserved children.⁵⁶ It can also improve access to specialists, and can be as effective as in person visits for asthma specialist evaluations.^{57,58}

Over the past 15 years, we have established strong partnerships with Rochester city schools, providers, and the Rochester community, which have allowed us to implement and evaluate programs for urban

children with asthma. Similar to our prior school-based studies, this current intervention uses a system change to improve the delivery of asthma care. However, it is unique because it targets a particularly high-risk population for whom advanced treatment is needed (urban children with moderate-severe, poorly controlled asthma), and uses telemedicine technology to facilitate access to optimal specialist-directed guideline based step-wise care, in partnership with PCPs and the child's medical home to ensure coordination of care. We will use school-based and video supported DOT to ensure adherence to prescribed therapies. We anticipate that uniting care across settings will optimize treatment for traditionally underserved children with asthma, and ultimately reduce disparities.

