The study team nurse will review telemedicine visit records after each visit to ensure completion by the specialist provider within 3 days, and to assess delivery of guideline-based care. Any concerns will be relayed back to the specialist provider. We will track delivery of medications, DOT, and show rates at needed in-person visits. We will also ensure ongoing communication with the PCP.

Subgroup of Teens

For a small subgroup (approximately 10-30 teens), we will test the feasibility of conducting the TEAM-UP intervention with teens. This subgroup will not be randomized. For all teens, we will initiate a telemedicine visit conducted within the school (or home) with an asthma specialist. Two follow-up visits will occur either with an asthma specialist or with an asthma nurse educator, to re-assess symptoms and ensure guideline-based care is implemented appropriately. As routine within the Telemedicine Program, the teen's PCP will be notified of all visits, severity of child as documented within the telemedicine visits, and any changes in care that are recommended through this program. Unlike the study for younger children, we will not implement DOT of medications as part of the program for teens, although the telemedicine provider may suggest DOT in their asthma care recommendations.

Enhanced Care (EC) Comparison Condition:

Similar to the TEAM-UP group, children in the EC group will receive a symptom assessment and asthma education materials at baseline, and we will contact the PCP by facsimile or email and will recommend daily preventive asthma medication as well as a referral to specialist. However specialist visits will not be facilitated through the study. We will also give providers a summary of the national asthma guidelines and a list of community resources including the Healthy Homes Partnership and the New York State quitline. We will provide systematic reminders to the family and PCPs to schedule recommended healthcare visits at the same intervals as the TEAM-UP group's telemedicine visits. Participants will not be blinded to group allocation; they will be told that they are randomly assigned to 2 different ways of approaching asthma management. In all of our prior studies, the EC group improved over time, creating a conservative bias.

Follow-Up Assessments:

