There may be some cost to participate in this study. Participants will be responsible to purchase medications and spacers during the study, including those used for DOT of asthma therapy. Participants may be charged for using data on their smartphone in accordance with their personal phone data plan and rates. Participants randomized to the TEAM-UP group will also be responsible for any fees associated with telemedicine visits (e.g., co-pays etc.) completed through the study (these are medical processes that should occur according to the national guidelines regardless of the child's participation in the study). Based on our prior work with this population, we anticipate that most of the children will have some form of health insurance to cover the costs of visits and medications with minimal or no co-pay fee. In our prior studies we found that approximately 70% of families in the RCSD were insured with Medicaid which often eliminates co-pay fees for medications and care. If a child (in either group) does not have insurance, the study team will help the family secure health insurance. If a child in either group is unable to obtain health insurance and reports difficulty with associated medication costs, the study team will pay for the participant's medication and spacer for the program, as needed. If there is no insurance reimbursement for the telemedicine visit, subjects will not be asked to pay any additional costs. Participants and their insurance company will be responsible for the costs of all standard of care office visits and additional medications prescribed by their PCP.

Data Storage and Confidentiality:

To maintain the integrity, security, and confidentiality of study data, the data will be maintained in a secure and encrypted web-based database and/or a password protected database on a secure university network drive. No subject data will be stored on the internal hard drives of any University of Rochester computers. After data validation and analysis, subject information will be de-identified. All consent forms, paper surveys and additional correspondence will be stored in a locked filing cabinet in a locked hallway or locked office, and will only be accessible by the study staff.

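### Programme cost enters both cost formulas undifferenced and unitemised, so they match the plan's between-group definition only if it is read as an incremental cost, and no rule keeps payer-billed telemedicine visits out of two terms of the ICER

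*Combined protocol and SAP*

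**What the plan says.** The Cost Effectiveness Analysis section opens with two outputs. One is a budget-type figure: "We will consider the total cost of initiating and maintaining the program". The other is the ICER, which it defines in words: "The ICER is the difference in cost between the 2 study groups", relative to the difference in SFD. The societal formula then adds ΔMedical, ΔProductivity and Program and divides by ΔSFD, with Δ stated to be TEAM-UP minus EC. Program has no Δ. (The numerator is printed without brackets; I read it as bracketed.)

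For the Medicaid perspective, net monetary benefit is ΔMedical minus Program. Here "The cost is equivalent to the cost of the program", again without differencing. The medical-cost difference is to "account for a potential reduction in unplanned visits as well as an increase in preventive visits".

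No list of what Program contains appears anywhere. Other sections bear on it:

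- **EC content.** Under All Study Children, PCPs in both arms are contacted with recommendations. Under Randomization, all families receive an education packet. The Enhanced Care (EC) Comparison Condition section adds a guideline summary and a resource list for providers, and states: "We will provide systematic reminders to the family and PCPs to schedule recommended healthcare visits". Potential Benefits puts the number of reminders to EC families at three.
- **Study-paid drugs.** Under Compensation, the study pays for medication and spacers for a child in either arm who cannot obtain insurance.
- **Telemedicine visits.** Process Evaluation counts them among the programme's components. Background states: "Telemedicine visits are reimbursed by local payers, including Medicaid Managed Care". Under Compensation, TEAM-UP families "will also be responsible for any fees associated with telemedicine visits".

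**The concern.** The verbal definition calls for a difference between arms in every cost element. The formula takes that difference for two elements and not for the third, although the comparator is not a zero-delivery arm. If an analyst enters what TEAM-UP costs to run, whatever the study spends on delivering EC is never subtracted, and TEAM-UP looks dearer than it is relative to EC.

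There is a second exposure. The specialist telemedicine visits are what the programme delivers, but they also generate claims that belong in medical cost. With no allocation rule, the same three visits per child could be picked up in programme costing and again in utilisation data.

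At stake are the ICER, which is the main outcome of the societal analysis, the acceptability curve built on it, and the Medicaid net benefit. These are the evidence for the study objective on cost-effectiveness and sustainability. Two analysts following the section faithfully could report different results from the same data, with the choice made after costs are known.

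**Working it through.** The section states no unit cost, programme cost, expected ICER or threshold, so there is no figure to reproduce. The check is algebraic, followed by an illustration on assumed costs.

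**Step 1: programme term.** Per child, let S be the study-delivered cost common to both arms, T the TEAM-UP-only cost and E the EC-only cost. TEAM-UP's programme cost is S + T and EC's is S + E. The verbal definition requires (S + T) − (S + E) = T − E. With assumed values T = $200, E = $30 and S = $80:

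| Meaning given to Program | Amount entered | Excess over T − E = $170 |
|---|---|---|
| Incremental cost, T − E | $170 | $0 |
| TEAM-UP-only items, T | $200 | E = $30 |
| Gross TEAM-UP cost, S + T | $280 | S + E = $110 |

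Formula and definition agree only in the first row. In the second, shared items cancel and the error is E. In the third, the error is EC's whole programme cost.

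On the documents, the baseline symptom assessment, education materials and PCP contact belong to S. The reminders belong to E. The provider guideline summary and resource list are described only under EC and appear to belong to E.

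**Step 2: visits.** TEAM-UP has 3 telemedicine visits (one initial, two follow-up). If each is valued at c and enters both ΔMedical and Program, the ICER numerator is too large by 3c.

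**Step 3: scale of the ICER shift.** An excess X per child moves the ICER by X/ΔSFD. The power section uses differences of 0.7 and 0.8 SFD but does not state the recall window. Two scales are shown: the difference as given, and annualised on an assumed 14-day window with a constant effect all year (0.7 × 365/14 = 18.25; 0.8 × 365/14 = 20.86). All costs are assumed.

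| Excess X per child | X/0.8 to X/0.7 | X/20.86 to X/18.25 |
|---|---|---|
| EC cost omitted, $10 | $12.5 to 14.3 | $0.48 to 0.55 |
| EC cost omitted, $50 | $62.5 to 71.4 | $2.4 to 2.7 |
| EC cost omitted, $100 | $125 to 143 | $4.8 to 5.5 |
| 3 visits at $50 = $150 twice | $188 to 214 | $7.2 to 8.2 |
| 3 visits at $100 = $300 twice | $375 to 429 | $14.4 to 16.4 |
| 3 visits at $200 = $600 twice | $750 to 857 | $28.8 to 32.9 |

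The two scales differ by 365/14 = 26.1, so the assumed scale matters as much as the assumed cost.

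**Step 4: Medicaid net benefit.** Omitting EC's programme cost lowers the net benefit by that cost per child, whatever the sign of the medical term. Visits behave differently. With Δ = TEAM-UP minus EC and $300 of billed visits, the contribution to net benefit is:

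- as printed, visits in both terms: +300 − 300 = $0;
- as printed, visits in ΔMedical only: +$300, a cost counted as a gain;
- medical term written as savings (EC minus TEAM-UP), visits in both terms: −300 − 300 = −$600;
- medical term as savings, visits in the medical term only: −$300, the correct charge.

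So allocating visits to the medical term works in this formula only once the medical term is written as savings.

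**The case against.** The best defence is that Program is undefined and sits directly after a sentence defining the ICER as a between-group difference, so it can be read as the incremental programme cost. Definition and formula then agree. That reading is available, and it rules out saying the plan does charge TEAM-UP everything and EC nothing.

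A reader might take the total cost of initiating and maintaining the programme as the definition of Program. The sentence does not support that: it announces total cost alongside the ICER, as a separate output.

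A reader might also infer that visits are counted twice. No text places billed visits in Program. Preventive visits are named within the medical difference, and Program could consist of unbilled work such as the training, medication delivery and DOT tracked in the Measures table. Against that, Process Evaluation does list the visits as a programme component, and no rule excludes them. The risk stands; the fact is not established.

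Finally, most EC content is notices and reminders, much of it shared with TEAM-UP, so the EC-only cost may be small. That also stands. What the defence does not supply is any text telling the analyst which reading to use.

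**Conclusion.** The point holds as a mismatch between the plan's verbal definition and its formulas, together with a missing allocation rule. Taken literally as TEAM-UP's programme cost, Program overstates incremental cost by EC's programme cost. Taken as TEAM-UP-only items, it overstates it by EC-only items, chiefly the reminders. Taken as incremental cost, there is no error. With a positive ΔSFD, both possible errors in the ICER make TEAM-UP look less cost-effective.

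The size cannot be stated from the documents. Every dollar amount above is assumed, as are the 14-day window, the constant effect over the year, and full completion and billing of the three visits.

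A tempting further inference, that the Medicaid net benefit is understated by the value of visits entered twice, fails on the formula as printed, because such visits cancel there. It would hold only after the sign of the medical term is changed.

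This concerns a secondary economic analysis; the primary SFD comparison is untouched. The correction is still worth making before costs are known.

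**What to change.** - In both formulas, replace Program with ΔProgram, defined as study-delivered programme cost per child, TEAM-UP minus EC, and bracket the ICER numerator.
- Itemise it. Cost EC-specific delivery (reminders, guideline summary, resource list) on the same basis as TEAM-UP delivery, and let items common to both arms cancel.
- Assign every payer-billed visit or drug to the medical term only. State where unreimbursed telemedicine visits and study-paid medication or spacers go, applying the same rule in both arms.
- In the Medicaid net benefit, make this change together with writing the medical term as savings (EC minus TEAM-UP). Done alone, it would leave a billed visit counted as a gain.
- Keep total start-up and running cost as a separately reported figure, as the section already intends.

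The cost is a few sentences in the economic section and some extra costing of EC staff time and materials. If incremental cost was meant all along, the change to the programme term only records it.

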3. To randomly allocate subjects into either: 1) TEAM-UP intervention group (directly observed administration (DOT) of preventive asthma medications and ongoing monitoring and tailoring of the care regimen using telemedicine directed by specialist care) or 2) a control condition including enhanced care (EC) (Report of symptoms to PCP, recommendations to initiate preventive medications and make a specialist referral). (Subset of 12-16 year olds will all receive specialist care through telemedicine.)
4. To follow subjects prospectively throughout one year for endpoints defined by clinical outcomes (symptom severity, asthma control, and health care use), functional outcomes (absenteeism, quality of life), airway inflammation (FeNO), FEV1, and healthcare utilization. (Subset of 12-16 year olds will be followed for approximately 3 months.)

5. To assess the effectiveness of the TEAM-UP intervention in reducing asthma morbidity (including symptom-free days post-intervention as the primary outcome) compared to an enhanced care (EC) comparison group in school age children with moderate-severe asthma.
6. To assess the effectiveness of TEAM-UP in improving guideline-based asthma care (corrective actions; step-wise medication adjustments, identification and treatment of allergies or other co-morbid conditions) vs. EC.
7. To establish the cost-effectiveness of the intervention with a specific focus on ultimate sustainability and dissemination.
8. To evaluate the process of program implementation (i.e., convenience, scheduling, satisfaction, etc.)

Study Overview:

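### The Medicaid net monetary benefit formula has the wrong sign on ΔMedical under the plan's only definition of Δ

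*Combined protocol and SAP*

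**What the plan says.** The formulas are in the Analysis part of the combined protocol and SAP, under Cost Effectiveness Analysis. Two evaluations are planned.

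- **Societal perspective.** The main outcome is an ICER whose cost side is "\Delta\text{Medical} + \Delta\text{Productivity} + \$\text{Program", divided by the difference in symptom-free days. The symbol is defined there: "where $\Delta = (\text{TEAM-UP}) - (\text{EC", that is, TEAM-UP minus EC. I found no other definition of Δ in the document.
- **Medicaid perspective.** A cost-benefit approach is used. The benefit is described in words: "Benefits include the net difference in medical costs between children in TEAM-UP and EC". It is to "account for a potential reduction in unplanned visits as well as an increase in preventive visits". On the cost side, "The cost is equivalent to the cost of the program". The formula is "Net Monetary Benefit* = $\Delta\text{Medical} - \$\text{Program".

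Objective 7 under Study Objectives is "To establish the cost-effectiveness of the intervention with a specific focus on ultimate sustainability and dissemination". In the Background, the sustainability of the telemedicine programme is tied to payment: "Telemedicine visits are reimbursed by local payers, including Medicaid Managed Care".

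**The concern.** One symbol does two opposite jobs in the same section. In the ICER, ΔMedical is added to programme cost, so it is a cost difference and a saving makes it negative. In the Medicaid formula it stands as the benefit, from which programme cost is subtracted. With Δ as defined, the Medicaid formula penalises savings and rewards extra spending.

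This is the only formula given for the Medicaid perspective, and payer support bears on the sustainability question in objective 7. The result itself may not reveal the error. The plan expects effects in both directions: fewer unplanned visits but more preventive ones. The TEAM-UP Intervention section also allows for treatment step-ups, allergy testing, biologics and further evaluations, which could raise medical cost. Neither sign of ΔMedical would look implausible to an analyst.

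**Working it through.** **Inputs from the plan**

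- D = ΔMedical = medical cost in TEAM-UP minus medical cost in EC.
- P = programme cost, taken as greater than zero.
- ICER cost side: D + ΔProductivity + P. I read the whole sum as the numerator, as the prose definition of the ICER requires.
- Printed Medicaid formula: D − P.

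The plan gives no monetary amounts, so there is no stated figure to reproduce. It also does not say whether costs are per child or in total. I use per child below; the algebra is the same for totals.

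**Consistent formula.** Without productivity, the payer's net cost from the ICER numerator is D + P. Net benefit is its negative:

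consistent = −(D + P) = −D − P

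**Size of the error**

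printed − consistent = (D − P) − (−D − P) = 2D

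The two agree only at D = 0.

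**When the verdict reverses**

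- D < −P (savings exceed programme cost): consistent is positive, printed is negative. A true gain is shown as a loss.
- D > P (extra medical cost exceeds programme cost): consistent is negative, printed is positive. A true loss is shown as a gain.
- |D| < P: both are negative, and only the amount is wrong.
- |D| = P: one of the two is exactly zero.

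**Illustration (USD per child; all amounts are assumptions)**

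| P | D | Printed, D − P | Consistent, −D − P | Printed − consistent | Verdict reversed? |
|---|---|---|---|---|---|
| 200 | −500 | −700 | +300 | −1,000 | yes |
| 200 | −200 | −400 | 0 | −400 | boundary |
| 200 | −100 | −300 | −100 | −200 | no |
| 200 | 0 | −200 | −200 | 0 | no |
| 200 | +100 | −100 | −300 | +200 | no |
| 200 | +200 | 0 | −400 | +400 | boundary |
| 200 | +500 | +300 | −700 | +1,000 | yes |
| 500 | −1,000 | −1,500 | +500 | −2,000 | yes |
| 500 | −200 | −700 | −300 | −400 | no |
| 500 | +200 | −300 | −700 | +400 | no |
| 500 | +1,000 | +500 | −1,500 | +2,000 | yes |

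A numerical check over a grid (P from 1 to 393, D from −1,000 to 998) found no exception to the size of the error, 2|D|, or to the condition for reversal, |D| > P.

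**The case against.** The strongest reply is that the definition of Δ is attached to the ICER and need not carry over. The Medicaid formula comes later, for another perspective and another method. The prose around it names a benefit and a cost, so benefit minus cost is the right structure. The first component of the benefit it lists is a reduction in unplanned visits. If ΔMedical there means savings, the printed line is correct, and the defect is one symbol used in two senses rather than a mistaken method. An analyst who reads the preceding sentences would probably see what was meant.

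Much of this stands. Savings were probably intended, and nothing in the plan shows that anyone would apply the line literally or that medical cost differences would exceed programme cost. The link from the Background's remark on reimbursement to this formula is also an inference, because that remark does not mention net benefit.

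It does not remove the problem. The prose speaks of a difference between TEAM-UP and EC without saying which is subtracted from which, so it does not replace the stated definition. If the savings reading is right, ΔMedical has opposite signs in two formulas of one section and the reader is not told. On either reading the text needs correcting.

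**Conclusion.** The concern holds. Under the only definition of Δ in the plan, the Medicaid formula has the wrong sign on ΔMedical. The error is 2 × ΔMedical, and the gain-or-loss conclusion reverses only when |ΔMedical| exceeds programme cost. These results are algebraic and need no cost data. The dollar examples and the per-child unit are assumptions, so how large the error would be in this trial cannot be stated.

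The scope is narrow. The ICER, the primary analysis of symptom-free days, the sample size and the type I error rate are unaffected. It should still be fixed, because a prespecified formula serving a named objective gives a wrong answer when followed as written.

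**What to change.** Keep Δ as TEAM-UP minus EC throughout and write:

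Net monetary benefit = −ΔMedical − programme cost = (medical cost in EC − medical cost in TEAM-UP) − programme cost.

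If the opposite difference was meant for the Medicaid analysis, the printed form can stay, provided the saving is defined there as EC minus TEAM-UP, preferably under its own symbol. It would also help to state whether the amounts are per child or in total.

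The cost is one formula line, with no change to data collection, design or the primary analysis.
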